Biodentine new bioactive calcium silicate-based cement has been recently launched in the dental market as a 'dentin substitute'. This new biologically active material facilitates its penetration through opened dentinal tubules to crystallize interlocking with dentin and provide mechanical properties. Biodentine has been developed using MTA based cement technology and hence; added improved properties such as physical qualities and handling, and its wide range of recommended applications in endodontic repair and pulp capping. [16]

Radiographic imaging of the dentoalveolar complex has been assessed using conventional periapical radiography, the benchmark for intraoral radiographic imaging for decades. Their known limitations of image magnification, distortion, superimposition and overlap of anatomy always led to unclear and misrepresentation of structures. Although the advent of digital intraoral radiography didn't improve these limitations, it provided a more active image manipulation than the film-based radiographs and reduced patient exposure

substantially. [17, 18]

7 - Objectives and hypothesis:

The objective of this prospective randomized clinical trial is to compare the clinical / radiographic outcomes of MTA and Biodentine as pulpotomy biomaterials used in apexogenesis treatment of symptomatic / asymptomatic vital immature mandibular permanent first molars with carious pulp exposure.

8-Trial Design:

Randomized clinical trial (RCT), parallel groups with 1:1 allocation ratio, Triple blinded (patient, clinical and radiographic assessor of the results and statistician)

III- Methods:

9-Study settings:

This study will be carried out on patients attending the outpatient clinic in Pediatric Dentistry department, Faculty of Dentistry, Cairo University, Egypt. the procedures will be carried out by [name] Associate Professor of Pediatric Dentistry in Pediatric Dentistry clinic. expected time duration from 2017 to 2018.

10- Eligibility criteria:

Inclusion criteria:

- Medically free children.
- Bilaterally Symptomatic / asymptomatic vital immature mandibular first permanent molars (with clinical carious exposure of the pulp and presence of bleeding upon exposure)
- Patients with an age range from 7-8 years.
- Absence of sinus tract, soft tissue swelling.

The exclusion criteria:

- Molars were excluded if non-restorable.
- excessive mobility (more than 1 mm horizontally).

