None needed.

12- Outcomes:

	Outcome	Tool/Device	Unit
Primary Outcome	spontaneous pain, sensitivity to percussion/ palpation)	Pain questionnaire	Binary
	Swelling or sinus tract	Visual examination by the third author	Binary
	Mobility	Back of the mirror	Binary
Secondary outcome	Stage of root development	Standardized periapical	3 stages
	Crown: Root ratio	Standardized periapical	2:1 ≥2:1
	Apex	Standardized periapical	Blunder apex, partially open, constricted
	Presence of radiolucency	Standardized periapical	Binary

Primary outcome:

Clinical assessment of the findings in the table will be conducted at follow up intervals (baseline, 6, 12 and 18 months)

Secondary outcome:

Radiographic assessment of stage of root development, crown: root ratio, apical closure and presence of radiolucency will be conducted through digital periapical radiographs by parallel

technique using film holders. The assessments will be carried out at follow up intervals (baseline, 6, 12 and 18 months)

13- Participants timeline:

	Study period				
	Enrolment	Allocation	Post allocation		Close out
Time point	For 7 months	0	6 months	12 months	18 months
Enrolment:					
Eligibility screen	✓				
Informed consent	✓				
History taking	✓				
Clinical examination	✓				
Preoperative radiograph	✓				
Allocation		✓			
Interventions:					
Access preparation		✓			
Placement of Biodentine (experimental group)		✓			
Placement of MTA (Control group)		✓			
Final restoration		✓			
Assessment					
Periapical radiograph as baseline reference			✓	✓	✓

Clinical examination to assess pain, swelling, fistula, tooth mobility			✓	✓	✓
Periapical radiograph to assess stage of root development, crown: root ratio, apical closure and presence of radiolucency			✓	✓	✓

14- Sample size calculation:

Sample size is calculated based upon the results of Alqaderi et al (2014) [15] who reported clinical success rate (primary outcome) for MTA = 90%. Since no relevant literature reported the clinical success rate of Biodentine in permanent teeth of pediatric patients, the success rate was assumed to be 50%. Using alpha level = 0.05 and β level = 0.20 (80% Power); the minimum estimated sample size will be 20 subjects per group for a total of 40 subjects. To compensate for a drop-out rate of 15%, the number is increased to 23 subjects per group for a total of 46 subjects.

Sample size calculation was performed using IBM® SPSS® Sample Power® Release 3.0.1.

15- Recruitment:

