All patients attending the outpatient clinic in pediatric dentistry department complaining from carious mandibular first permanent molars will be screened and enrolled in the study if they meet the eligibility criteria.

16- Allocation:

Sequence generation:

Access cavity prepared molars will be assigned into experimental or control group using simple randomization 1:1 by the help of the computer software(random.org).

Allocation concealment mechanism:

Numbered opaque sealed envelopes.

Implementation:

The child will choose an envelope randomly and open it after caries removal so that the operator knows which pulpotomy agent will be used only after finishing the access cavity. Sequence generation will be done by the third author and the patient assignment will be done by the operator.

17- Blinding:

Patients and their parents, the assessor and the statistician will be blinded.

18- Data collection methods:**Primary outcome:**

Clinical assessment of the following findings:

1. postoperative pain: through asking the child and the parent if there is pain either continuous or intermittent
2. Swelling: through visual examination by the assessor either intraorally or extra-orally.
3. Sinus or fistula through visual examination of the gingiva by the assessor.
4. Tooth mobility: By the back of the mirror checked by the assessor to detect mobility in any direction

This assessment will be conducted every follow-up visit throughout the study period at baseline, 6, 12 and 18 months.

Secondary outcome

Radiographic assessment to detect stage of root development, crown: root ratio, apical closure and presence of radiolucency through standardized periapical radiograph by parallel technique using film holder. This assessment will be conducted every follow-up visit throughout the study period at baseline, 6, 12 and 18 months.

Postoperative records will be performed by the assessor to avoid individual variability and to promote data quality.

19- Data management:

Explanation to the parents about the importance of the follow-up visits in addition to treatment of other dental problems are plans to promotes participants retention and complete the follow-up. Also, phone calls before the dates before the next follow-up visit will be scheduled.

All findings will be documented in the examination sheet then transferred electronically to computer in secured lace sequentially.

20- statistical methods:

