All data will be collected, checked, revised, tabulated and entered into the computer. Qualitative data will be presented as frequencies and percentages. Since the study is a split-

mouth design; Wilcoxon signed-rank test will be used to compare between the two groups. Friedman's test will be used to study the changes by time within each group. Kaplan-Meier survival curve will be constructed to calculate the mean survival estimates of the two groups. Comparison between survival times will be performed using Log rank test.

The significance level will be set at $P \leq 0.05$. Statistical analysis will be performed with IBM® SPSS® Statistics Version 20 for Windows.

21-Monitoring:

The study data and results will be monitored regularly by the assessor who will have full access to these data.

22- Harms:

No reported adverse effects for both testing pulpotomy agents. Any adverse events appear during the trial will be recorded, documented and treated.

23-Auditing:

Auditing of the study design will be done by the evidence-based committee, Faculty of Dentistry -Cairo University.

V- Ethics and dissemination:

24-Research ethics approval:

This protocol and the template informed consent form will be reviewed by the Ethics Committee of Scientific Research - Faculty of Oral and Dental Medicine - Cairo University.

25-Protocol amendments:

Any modification to the protocol which may have an impact on the conduction of the study, potential benefit of the patient or my affect patient safety including, the changes of study objectives, study design, sample size or significant administrative aspects will require a formal amendment to the protocol.

26-Consent and Assent:

Researcher will discuss the trial with legal guardian of each participating child. They will be able to have an informed discussion with the researcher after explaining the procedure in simple words. Verbal assent will be taken orally from the participating child while written consent will be taken from the legal guardian of each participating child who is willing to participate in the

® IBM Corporation, NY, USA.

® SPSS, Inc., an IBM Company.

trial. All consent forms will be translated into Arabic.

27-confidentiality:

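### One assessor records both the clinical and the film findings at each visit, and the stated blinding does not say it covers visit order, earlier scores or clinical signs

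*Combined protocol and SAP*

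**What the plan says.** Section 18 sets the timing of the film assessment: "This assessment will be conducted every follow-up visit throughout the study period at baseline, 6, 12 and 18 months". The same sentence is used for the clinical assessment. No pooled or end-of-study reading is described.

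Section 18 also places both kinds of finding with one role. The assessor does the clinical examination, for example "Sinus or fistula through visual examination of the gingiva by the assessor". At the end of the radiographic paragraph it adds: "Postoperative records will be performed by the assessor to avoid individual variability and to promote data quality". The tables in Sections 6 and 12 identify the examiner for swelling and sinus tract: "Visual examination by the third author". No separate film reader is named.

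On blinding, Section 8 says "Triple blinded (patient, clinical and radiographic assessor of the results and statistician" and Section 17 says "Patients and their parents, the assessor and the statistician will be blinded". Neither says what is concealed. Section 21 adds: "The study data and results will be monitored regularly by the assessor who will have full access to these data".

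Section 20 uses Friedman's test for change over time within each group and the Wilcoxon signed-rank test between groups. The radiographic outcomes are secondary.

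**The concern.** Root stage and apex (three categories each) and radiolucency (yes or no) are judgements made on an image. Two kinds of knowledge can influence them, and masking the material removes neither.

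- **Visit order and earlier scores.** A reader who expects roots to mature may be reluctant to record a lower stage than last time. Reading errors then stop cancelling out and accumulate in one direction.
- **Clinical signs.** A reader who knows that a molar is painful or swollen may call a doubtful shadow a radiolucency more readily.

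The research question asks about clinical and radiographic success together. If the film reading borrows from the clinical examination, the second result is no longer independent confirmation of the first. The plan includes no repeat reading or agreement check that would show how large the influence is.

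**Working it through.** **Inputs from the plan.** Section 14: success 90% (MTA) and 50% (Biodentine, assumed), so failure 10% and 50%; 20 per group, raised to 23 per group, 46 in total. Section 18: four assessment times. Section 12: three root stages.

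**The plan's own figure.** With the pooled two-sided formula and mean proportion 0.70:

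n = [1.96 × √(2 × 0.70 × 0.30) + 0.8416 × √(0.90 × 0.10 + 0.50 × 0.50)]² / 0.40² = (1.270 + 0.491)² / 0.16 = 19.4, so 20 per group. Then 20 × 1.15 = 23. Both reproduce. This point disputes neither, and a masked reading would not change them.

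**Visit order: simulation with assumed error rates.** There are 20 molars and four films, and every molar is truly at the middle stage throughout. Each reading is off by one stage, up or down with equal chance, with total probability 10%. When a reading falls below the previous recorded stage, the reader replaces it with that stage with probability s. A tie-corrected Friedman test is applied at 0.05.

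| Share of apparent regressions suppressed (s) | Falsely significant |
|---|---|
| 0 (independent reading) | about 4% |
| 50% | 7–9% |
| 75% | about 17% |
| 90% | about 33% |
| 100% | 51–54% |

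Ranges are the spread over separate runs. With full suppression, 5% reading error gives about 14% and 15% error gives 81–82%. With 23 molars, 10% error and full suppression the figure is about 64%. Both the error rate and s matter, and the documents give neither.

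**Visit order: between materials.** The full-suppression model was applied equally to two identical arms (20 pairs, 10% error) and tested with Wilcoxon signed-rank on the 18-month stage. The false-positive rate was 5.3%, which is essentially nominal.

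**Clinical signs and radiolucency.** Let c be the assumed share of clinically failed molars without a lesion that are called radiolucent because of their signs. Let L be the share of failed molars that truly have a lesion, taken as equal in both arms.

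Spurious difference = c × (1 − L) × (0.50 − 0.10)

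- c = 0.20, L = 0: 0.20 × 1 × 0.40 = 0.08, or 8 points, the ceiling for this c.
- c = 0.20, L = 0.5: 0.20 × 0.5 × 0.40 = 0.04, or 4 points.
- c = 0.10, L = 0: 0.10 × 1 × 0.40 = 0.04, or 4 points.

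**Size of a re-reading.** 46 molars × 4 films = 184 images. If both molars of 46 children are used, 2 × 46 × 4 = 368. Both are shown because Section 8 describes parallel groups and Section 20 a split-mouth design.

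**The case against.** The strongest reply is that the plan is silent rather than wrong. It does not say that a film is scored straight after the examination, or that earlier scores are in view. Assessing at every visit fixes the time points and does not exclude a later reading of stored digital images. The assessor is declared blinded. This stands: a reader might infer that the assessor scores each film having just examined the child, but that is not stated.

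Second, the trial compares materials, and visit-order knowledge acts alike on both arms if masking to material holds. This also stands, and the two-arm check confirms it. The large Friedman figures must not be read as bias between MTA and Biodentine.

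Third, no growth over 18 months in immature molars of children aged 7–8 is implausible. If 20% of molars truly advance per interval, independent reading at 10% error already gives a significant Friedman test in 93% of runs. The practical harm is therefore overstated growth rather than a false finding that roots grew at all. The figure above 50% also needs a reader who never records a regression.

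Fourth, the films are standardised with a holder, the categories are coarse, the outcomes are secondary, and reading serial films in order is a recognised choice. These points reduce the size of the problem. They do not supply the missing statement, and full access to data and results under Section 21 makes it harder to assume that earlier findings are withheld.

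**Conclusion.** The point holds as a gap in the plan. One assessor is given both kinds of record at each visit and has full data access, and the blinding statements do not mention visit order, earlier scores or clinical signs. The film readings may therefore be influenced by them. That they will be is not shown.

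For change over time, the effect is overstated growth in the within-group Friedman analysis. Under the no-growth model it runs from negligible to severe according to how strongly regressions are suppressed. For the comparison between materials, visit order adds no inflation provided masking to material holds. Clinical signs can carry part of a clinical difference into radiolucency: at most 8 points at 20% over-calling, and less where failed molars truly have lesions. A reader might infer that the whole clinical difference is copied across. These figures do not support that, since 8 points is one fifth of the 40-point difference assumed in Section 14, and the 50% rate there was adopted for want of literature.

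A reader might also infer that the assessor knows the material, because Section 16 says "Sequence generation will be done by the third author" and the third author is the named clinical examiner. That deserves its own clarification. The documents do not say that this person learns which child received which material, and this point does not depend on it.

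Because the outcomes are secondary and the remedy is cheap, the change is worth making but is not critical to the trial.

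**What to change.** Keep the readings made at visits for patient care. State in Section 18 that the analysed radiographic reading is a single one, made by the same assessor after the last visit from coded digital films, with identity, date, earlier scores and clinical record hidden and the 6-, 12- and 18-month films in random order. State in Section 17 that the assessor's blinding covers these items for that reading.

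Also state which film is the analysed baseline, since Section IV lists both a preoperative and an immediate postoperative film. If it is the preoperative film, acknowledge that it cannot be masked as to time: it shows no pulpotomy or restoration and is recognisable whatever its code. The contrast from that baseline to follow-up then stays partly unmasked, while the contrasts among follow-up films are protected.

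The cost is one extra reading session (about 184 images, or 368 if both molars of 46 children are used) and recoding of the files. No extra staff, visits, exposures or participants are needed. The remaining weakness is that the assessor may recall some films.

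### Sections 8 and 14 describe a parallel-group trial, Section 20 a split-mouth trial with a paired test, and nothing in the protocol says which is meant

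*Combined protocol and SAP*

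**What the plan says.** - **Section 8 (Trial Design):** "Randomized clinical trial (RCT), parallel groups with 1:1 allocation ratio".
- **Section 10 (Eligibility criteria):** requires "Bilaterally Symptomatic / asymptomatic vital immature mandibular first permanent molars". It does not say that both molars enter the study, or with which materials.
- **Section 14 (Sample size calculation):** success of 90% for MTA and an assumed 50% for Biodentine, alpha 0.05 and power 80%, from which "the minimum estimated sample size will be 20 subjects per group for a total of 40 subjects". For 15% dropout, "the number is increased to 23 subjects per group for a total of 46 subjects". No discordant proportion or within-child correlation is given.
- **Section 16 (Allocation), sequence generation:** "Access cavity prepared molars will be assigned into experimental or control group using simple randomization 1:1".
- **Section 16, implementation:** "The child will choose an envelope randomly and open it after caries removal", and then "the patient assignment will be done by the operator".
- **Section 20 (statistical methods):** gives the split-mouth design as the reason for its between-group test: split-"mouth design; Wilcoxon signed-rank test will be used to compare between the two groups".

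**The concern.** A parallel trial gives each child one material and compares two independent sets of children. A split-mouth trial gives each child both materials and compares them within the child. The two need different allocation rules, sample-size inputs and tests. The protocol takes its design label and sample size from the first and its between-group test from the second.

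Three things hang on the answer: whether the named test can be run at all, how many children must be recruited, and what the allocation list must contain. The last cannot be repaired once envelopes have been opened. Choosing between a paired and an unpaired test after the data are in would be a post hoc choice.

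**Working it through.** **Inputs.** From Section 14: success 0.90 and 0.50, alpha 0.05, power 80%, 20 per group, 15% dropout, 23 per group. Sidedness is not stated there; two-sided is used below. The within-child correlation (phi) appears nowhere in the protocol. It is assumed here to lie between 0 and 0.33, the largest positive value these rates allow.

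**1. The protocol's own figure.** Pooled formula for two independent proportions, mean proportion 0.70:

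n = [1.960 × √(2 × 0.70 × 0.30) + 0.842 × √(0.90 × 0.10 + 0.50 × 0.50)]² / (0.90 − 0.50)²

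= (1.270 + 0.491)² / 0.16 = 19.38, so 20 per group.

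The dropout step is 20 × 1.15 = 23. Section 14 therefore reproduces as a calculation for two independent groups, with no paired input.

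**2. What a paired calculation would need.** The probability that both molars succeed is 0.45 + 0.15 × phi, since √(0.90 × 0.10 × 0.50 × 0.50) = 0.15. The discordant cells are 0.90 and 0.50 minus that value, and pd is their sum. The number of pairs is [1.960 × √pd + 0.842 × √(pd − 0.16)]² / 0.16.

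| phi (assumed) | discordant cells | pairs for 80% |
|---|---|---|
| 0 | 0.45 / 0.05 | 22.0 |
| 0.15 | 0.4275 / 0.0275 | 19.8 |
| 0.30 | 0.405 / 0.005 | 17.6 |
| 0.33 | 0.40 / 0 | 17.1 |

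Rounded up, this gives 20 only for phi of about 0.14 to 0.20, a value Section 14 does not state.

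**3. Power if split-mouth with 23 children.** After 15% dropout, 23 × 0.85 = 19.55, so 19 or 20 pairs remain. On a binary outcome the signed-rank statistic reduces to (b − c)/√(b + c), where b and c are the two discordant counts. Section 20 does not say whether the p-value is asymptotic or exact, so both are shown, by enumeration over the discordant counts for phi 0 to 0.33.

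| Evaluable pairs | Asymptotic | Exact |
|---|---|---|
| 19 | 77–98% | 66–84% |
| 20 | 79–98% | 69–87% |
| 23 (no dropout) | 85–99% | 78–95% |

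With 46 children, power is not in question: 40 pairs give 97% or more with either version.

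**4. Power if parallel.** Enumeration of both binomials, two-sided 0.05.

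| Evaluable per group | Uncorrected chi-square | Fisher's exact |
|---|---|---|
| 19 | 82% | 71% |
| 20 | 84% | 74% |
| 23 (no dropout) | 88% | 81% |

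**5. Does Section 16 decide it?** It names molars as the unit assigned, then one envelope drawn by the child, then assignment of the patient. One envelope per child fits a parallel trial. It also fits a split-mouth trial if the opposite molar takes the other material, but the protocol does not say so.

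**The case against.** The best defence is that the trial is plainly split-mouth and the rest is loose wording. Section 20 states the design as a fact, Section 10 requires bilateral molars, and Section 16 assigns molars. On that reading 23 + 23 would be molars in 23 children. The lean is real, but it does not remove the conflict. Section 8 says parallel, Section 14 counts 46 subjects, Section 16 also speaks of patient assignment, and no sentence requires a child's two molars to receive different materials.

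Two stronger readings are tempting, and the documents do not support either.

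- **The trial is underpowered.** A reader might infer this from the mismatch. Whether power falls short depends on the design, on the test version and on a correlation the protocol does not give. Several combinations reach 80%.
- **Each molar is drawn independently.** A reader might take simple randomisation of molars to mean this. About half the children would then receive the same material on both sides and give no between-material pair: on average 11.5 of 23 children, or 23 of 46. This is a risk of the wording, since the text mentions one envelope for the child and describes no second draw. Any power figure for it would also need a rule for handling same-material children, which the protocol does not give.

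It is also fair to say that Section 14's arithmetic is sound for a parallel trial. The fault is that it does not belong to the analysis in Section 20.

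**Conclusion.** The point holds as an explicit contradiction in the current text and must be fixed before enrolment. The primary comparison cannot be matched to the stated sample size, and the number of children is uncertain by a factor of two.

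The effect on power is undetermined rather than shown to be harmful. It ranges from comfortable (46 split-mouth children) to below 80% (20 evaluable pairs with the exact signed-rank test at low correlation, or 20 per parallel group with Fisher's exact test). All power figures rest on 90% vs 50%, of which the 50% is the protocol's assumption, and on two-sided 0.05. The paired figures also rest on the assumed phi range. That the two designs conflict depends on none of these numbers.

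**What to change.** The sponsor states which design was meant and makes Sections 8, 14, 16 and 20 agree before enrolment.

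**If split-mouth:**
- Section 8: replace the parallel-group wording with a within-child, split-mouth description.
- Section 16: use one envelope per child that names which side receives which material, so the two molars always differ.
- Section 14: give children and molars separately. Restate power for the paired test, naming the asymptotic or exact version and the assumed discordant proportions.
- Section 20: keep the paired test and add a paired 95% confidence interval.

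**If parallel:**
- Section 16: randomise children, with one study molar each and a rule for which molar that is, given the bilateral criterion in Section 10.
- Section 20: delete the split-mouth wording and replace the signed-rank test with one pre-named test for two independent proportions.
- Section 14: the stated n and 80% power can stand with the uncorrected chi-square test. If Fisher's exact test is named, restate the power, which is about 71–74% at 19–20 evaluable per group.

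**Cost:** wording in four sections, one restated power calculation and, if split-mouth, an allocation list by child and side. Whether the number of children changes depends on what 46 subjects was meant to count.

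### Section 20 tests paired yes/no primary outcomes with the Wilcoxon signed-rank test, leaves the P-value version open, and plans no between-group difference in success with a confidence interval

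*Combined protocol and SAP*

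**What the plan says.** Section 12 lists three rows of primary outcome (pain or sensitivity, swelling or sinus tract, mobility), and the unit of each is binary. The radiographic outcomes include three-level ordered ones: stage of root development and state of the apex.

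Section 20 describes the study as split-mouth and on that ground says the "Wilcoxon signed-rank test will be used to compare between the two groups". The only other between-group test is the log-rank test. For description it says "Qualitative data will be presented as frequencies and percentages", and it adds Kaplan-Meier mean survival for each group. It does not say whether P values are exact or asymptotic. It names no between-group difference or ratio, and no confidence interval. The significance level is 0.05; whether tests are one- or two-sided is not stated.

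Section 14 sizes the trial on success rates. For MTA the cited study "reported clinical success rate (primary outcome) for MTA = 90" per cent; for Biodentine "the success rate was assumed to be 50" per cent. It concludes that "the minimum estimated sample size will be 20 subjects per group for a total of 40 subjects", raised to 23 per group for drop-out. Section 8 describes parallel groups.

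**The concern.** The signed-rank test ranks the sizes of within-pair differences. With yes/no outcomes a within-pair difference can only be -1, 0 or +1, so the non-zero differences are all tied and there is nothing to rank. What remains is a comparison of two counts: pairs where only one material failed, and pairs where only the other did. If software reports the asymptotic P, a normal approximation is being applied to what may be very few pairs.

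The more important gap does not depend on the version of P. The research question asks whether Biodentine is more successful than MTA, and the sample size is built to detect a 40-point gap. If the materials turn out close, the likely report is two percentages and a non-significant P. Nothing in the plan would then show how large a difference the data still allow, and the result could be read as showing that the materials are equally good.

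**Working it through.** **Inputs.** From Section 14: success 90% (MTA) and 50% (Biodentine, assumed), alpha 0.05, power 80%, 20 per group, then 23. Assumptions made here: two-sided tests, and each child supplies one molar to each group, so 20 or 23 per group means 20 or 23 pairs.

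**The plan's own figure.** Two independent proportions, pooled variance, no continuity correction, mean rate 0.7:

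n = [1.96·√(2·0.7·0.3) + 0.842·√(0.9·0.1 + 0.5·0.5)]² / 0.4² = [1.270 + 0.491]² / 0.16 = 19.4, so 20 per group. It reproduces, as a calculation for independent groups. 20 × 1.15 = 23 also reproduces.

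**What the signed-rank test becomes.** Let b and c be the two discordant counts and m = b + c. Every discordant pair has average rank (m+1)/2. The rank sum for one direction is b(m+1)/2, its null mean is m(m+1)/4, and its tie-corrected variance is m(m+1)²/16. Hence z = (b − c)/√(b + c), which is McNemar's test without correction. An exact signed-rank P on the same pairs equals the exact McNemar (binomial) P.

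**P values at small counts.** For 4-0: z = 4/√4 = 2, P = 0.0455. Exact P = 2 × (1/2)⁴ = 0.125. Mid-P counts half the probability of the observed split in each tail, giving 0.0625.

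| Split | Asymptotic | Mid-P | Exact |
|---|---|---|---|
| 4-0 | 0.046 | 0.0625 | 0.125 |
| 5-0 | 0.025 | 0.031 | 0.0625 |
| 7-1 | 0.034 | 0.039 | 0.070 |
| 15-6 | 0.0495 | 0.0525 | 0.078 |

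Over every split of up to 23 discordant pairs, the asymptotic P and the mid-P fall on opposite sides of 0.05 only at 4-0 and 15-6.

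**How many discordant pairs to expect.**
- Planned 90% versus 50%, independent molars: 0.9·0.5 + 0.1·0.5 = 0.50, or 10 of 20. Over all possible within-child correlations the range is 40% to 60%, or 8 to 12 of 20.
- Both at 90% (an assumption), independent molars: 2·0.9·0.1 = 0.18, or 3.6 of 20 and 4.1 of 23. Exactly 4 of 23 then has probability 21%.

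**Type I error, by full enumeration over b and c.**

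| | 20 pairs | 23 pairs |
|---|---|---|
| Asymptotic, both 90% | 4.0% | 4.5% |
| Asymptotic, maximum over discordance | 5.04% | 5.6% |
| Mid-P, both 90% | 1.4% | 1.8% |
| Mid-P, maximum | 5.04% | 4.9% |

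The 5.6% occurs at about 90% discordance. Given exactly 4 discordant pairs, the asymptotic test rejects 12.5% of the time under the null. With 23 pairs and both rates at 90%, that contributes 0.125 × 0.21 = 2.7 points of the 4.5% total.

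**Power at 90% versus 50%, independent molars.** 20 pairs: asymptotic 79.0%, mid-P 78.7%, exact 69.4%. 23 pairs: 84.9%, 84.8%, 77.7%.

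**What a non-significant result leaves open.** With discordance d, n pairs and an observed difference near zero, the 95% half-width is about 1.96·√(d/n). For n = 23: d = 0.18 gives 17.3 points and d = 0.30 (an assumption) gives 22.4 points. If the planned 46 subjects meant 46 children with a molar in each group, the half-widths would be 12.3 and 15.8 points.

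**The case against.** The strongest defence is that the named test does its job on average. Uncorrected McNemar is a conventional choice, and here its error rate is below 5% at realistic discordance. That stands. A reader might infer from the 4-0 example that the plan inflates the false-positive rate; the enumeration does not support this.

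A reader might also infer that the test will report too small a P. Section 20 does not say the asymptotic version will be used, and the exact version has no such problem. What stands is narrower: the version can decide the verdict and is not fixed in advance.

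Nor does the plan itself expect few discordant pairs. At its own rates about half the pairs are discordant, and exactly 4 of 20 would then occur about 0.5% of the time. The sparse case needs both materials near 90%, which the documents do not state. It remains worth covering, because Section 14 says the 50% was assumed for want of relevant literature.

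It is tempting to cite 5-0 and 7-1 as further results that would be overturned. They cross 0.05 only against the fully exact P; under the mid-P proposed here both stay significant.

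Finally, percentages per group are planned, so a reader can subtract them, and mean survival is planned too. But the interval for a paired difference needs the discordant counts, which group percentages do not give.

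**Conclusion.** The point holds as a modest fault in the choice of test and a more useful one in reporting. The signed-rank test is not suited to binary pairs, but the harm is confined to individual results, chiefly a 4-0 split, and arises only if the asymptotic P is used. The greater loss is that no paired difference with a confidence interval is planned. With 23 pairs and 18% to 30% discordance, a non-significant result leaves about 17 to 22 points either side of the estimate unexamined, and could be read as equivalence that the data do not show.

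This rests on two-sided testing, one molar per material in each child, 20 or 23 pairs and, for the sparse case, success near 90% with both materials. All of it depends on the design being split-mouth. If it is parallel, as Section 8 says, there are no pairs and neither the signed-rank nor McNemar's test applies.

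**What to change.** First reconcile Section 8 (parallel groups) with Section 20 (split-mouth), and say whether 23 per group means 23 children or 46.

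If split-mouth is kept, change Section 20 so that:
- binary outcomes are compared with McNemar's test, two-sided, using the mid-P, with the exact P shown alongside;
- the paired difference in 18-month clinical success is reported with a 95% CI by a named method for paired proportions (for example Newcombe or Tango), together with the discordant counts, and with a statement of how the listed clinical findings combine into success;
- the signed-rank test is kept for the three-level ordered radiographic outcomes.

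The cost is about two sentences; no visit, procedure or sample size changes. At 90% versus 50% with independent molars, mid-P loses 0.3 points of power at 20 pairs and 0.1 at 23. At the strongest possible positive correlation between a child's molars it loses more (98.4% to 94.9% at 20 pairs), but power there is ample. Relying on the exact P alone would cost 9.6 points at 20 pairs with independent molars (79.0% − 69.4% = 9.6), which is why mid-P is proposed for the decision.
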